In HVTN 115 Part A, the frequency of antigen-specific B cells in peripheral blood after the fifth dose of vaccine was similar in all groups, with a slightly higher frequency and response rate observed in the higher dose groups compared with the 20 mcg/dose group. In this pediatric study, the selection of lower doses is consistent with vaccine strategies for other pathogens where lower doses are often used. While this study will not be powered for a formal comparison between these arms, previous pediatric vaccine studies have demonstrated that immune responses induced by a lower dose of protein were comparable to or greater than those seen with the higher dose. In the malaria RTS,S vaccine regimen, a delayed fractional immunogen dose equal to 20 mcg induced higher antibody avidity and antibody somatic hypermutation as compared to the higher dose (41). The inclusion of the 5 mcg dose in this study will permit a comparison of antibody avidity with the 20 mcg dose in infants and with all doses (20, 100 and 400 mcg) in adult immune responses from the HVTN 115 study.

The inclusion of five doses of a single product with a placebo arm will allow for directly assessing safety and testing whether the neonatal immune system has characteristics favorable to lineage-directed vaccination strategies.

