6.1.2 Sample size calculations for immunogenicity

To address binding antibody endpoints, the analysis will descriptively summarize binding response positivity call rates to test superiority of IgG binding Ab responses for CH103-like CD4bs and V1V2 for comparisons versus zero using binomial exact tests with 5% type-I error rate each. Note that if in HIV-infected women, maternal antibodies that differentially bind to the CD4bs occur at a rate of 51% [estimated from n = 14 CAPRISA 002 women infected 2-3 years (76) and are transmitted to the infants, comparisons at early timepoints may be confounded by background positivity. Therefore, we have chosen the 2 weeks post 5th vaccination timepoint (~ one year) for the power calculation. By this time, both transplacental and breastmilk-associated antibodies (breast-feeding typically ceases at 6 months of age in the South Africa setting) are expected to have waned to below detectable levels, obviating the requirement to increase the placebo recipient sample size for a comparison with this high background rate. The following calculations assume a 25% rate of missing data to accommodate missingness at the 1-year timepoint.

The main goals of this trial regarding immunogenicity outcomes involve a preliminary estimation of rates of "response" (defined for Primary Endpoint 2 as initiation of either the CD4bs or the V1V2 B cell lineage) based on data from immune assays among vaccinees. No adjustment for multiple comparisons will be

made for the use of multiple assays. The precision with which the true response rate can be estimated from the observed data depends on the true underlying response rate and the sample size. Two-sided 95% confidence intervals for the response rate based on observing a rate of responses in the vaccinees is shown in Table 6-3. Calculations are done using the score test method (75). The n=13 assumes a 25% rate of missing immunogenicity data.

Table 6-3 Two-sided 95% confidence intervals for the true response rate based on observing a particular rate of responses in the vaccinees (n = 13)

No. of responses	Observed response rate (%)	95% Confidence interval
1/13	7.7	[1.4, 33.3]
2/13	15.4	[4.3, 42.2]
3/13	23.1	[8.2, 50.3]
4/13	30.8	[12.7, 57.6]
5/13	38.5	[17.7, 64.5]
6/13	46.2	[23.2, 70.9]
7/13	53.8	[29.1, 76.8]
8/13	61.5	[35.5, 82.3]
9/13	69.2	[42.4, 87.3]
10/13	76.9	[49.7, 91.8]
11/13	84.6	[57.8, 95.7]
12/13	92.3	[66.7, 98.6]
13/13	100	[77.2, 100]

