As a reference, the range of the lineage initiate response rates seen in adult participants in HVTN 115, Part A was 30%-40%, varying by dose. The sample size of n = 13 yields greater than 90% power to detect a response if the true rate is 30% or greater.

Group 7 is not powered for a formal immunogenicity analysis but is instead intended to provide data for a cursory investigation of immunogenicity of a variant regimen with a lower protein dose: (5 mcg instead of 20 mcg of protein). After an expected loss of 25% of immunogenicity data, the sample sizes of n = 4 for this group is sufficient to detect an extreme loss of immunogenicity due to the lower dose. If 0 of 4 participants in this group is a responder, the upper end of the 95% confidence interval for the true response rate for that regimen is 49%.

As shown in Table 6-4, there is low power for a formal comparison of immunogenicity response rates between the Group 3 and 5 pooled vaccine arms of size n = 13 versus a pooled placebo arm of size n = 8 after accounting for missingness. The sizes of differences that the trial is powered to detect are around 70%. These calculations use a Fisher's exact 2-sided test with a Type I error rate of 0.05. There is insufficient power for a formal comparison across the vaccine regimens or between Group 7 and the pooled placebo group.

Table 6-4 Power for comparison of response rates between 2 pooled arms (n1 = 8, n2 = 13)

	-	in Arm 2 in order to detect a rence
True response rate Arm 1 (%)	80% power	90% power
0	64	73
10	79	87
20	89	95
30	96	-

6.1.3 Considerations for comparison of immunogenicity to adults in HVTN 115

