using the mean and SD values from the HVTN 088 trial, the difference of 1.04 SD translates to a difference of 0.38 units of log10 binding magnitude; if one of the comparison groups has the same mean as was seen among non-negative values among vaccine recipients in the HVTN 088 trial (4.05 units), then after incorporating the expected 6% zero-valued (negative responder) measures, this corresponds to observing an increase or decrease in the overall mean from 3.78 in group 1 to 4.16 in group 2. These calculations assume a 15% loss-to-follow-up rate in HVTN 115 and a 25% rate in HVTN 135 and the (94%) response rate observed in the HVTN 088 vaccine recipients. The same approach will be used to test superiority of the magnitude of the IgG binding Ab response to each individual gp120 antigen in the panel.

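### Group 7: four evaluable infants cannot show an extreme loss of immunogenicity at the only lineage-response rate the protocol gives (30%-40%); secondarily, Table 6-4 is not the Fisher calculation it is said to be

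*Protocol*

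**What the plan says.** Protocol 6.1.2 defines response for the immunogenicity estimates: "defined for Primary Endpoint 2 as initiation of either the CD4bs or the V1V2 B cell lineage". As a reference for that response it reports that "the range of the lineage initiate response rates seen in adult participants in HVTN 115, Part A was 30%-40%, varying by dose", and it then gives the power of n = 13 at a true rate of 30%.

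The next paragraph turns to Group 7 (5 infants, 5 mcg protein). It first says that the arm is not powered for formal analysis and serves a cursory look. It then claims that, after 25% loss of data, "the sample sizes of n = 4 for this group is sufficient to detect an extreme loss of immunogenicity due to the lower dose". The support is one figure: with 0 of 4 responders, "the upper end of the 95% confidence interval for the true response rate for that regimen is 49"%. No comparator rate is given and extreme loss is not defined. Section 4.4.4 says of the 5 mcg and 20 mcg arms: "While this study will not be powered for a formal comparison between these arms".

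Table 6-4 in the same section gives detectable response rates for pooled placebo (n = 8) against pooled Groups 3 and 5 (n = 13). Its method is stated as follows: "These calculations use a Fisher's exact 2-sided test with a Type I error rate of 0.05". Its summary is "The sizes of differences that the trial is powered to detect are around 70"%.

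**The concern.** An upper limit of 49% for 0/4 shows a loss only if the rate without loss is clearly above 49%. The one rate the section offers for the defined response is below it. Zero responders is the most extreme result Group 7 can give, and at that rate it is compatible with no loss at all.

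Group 7 is the only arm with the lower protein dose, and Section 4.7.3 wants it in order to look for dose sparing. A reader who relies on the sentence could take 0/4 as evidence that 5 mcg lost immunogenicity when chance explains it well.

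The issue with Table 6-4 is smaller. A reader who enumerates the named test will not get the printed figures, and the dash says that 90% power is out of reach at a 30% placebo rate.

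**Working it through.** **Inputs.** Group 7: 5 enrolled, 25% missing, 5 × 0.75 = 3.75, taken as 4. Pooled Groups 3 and 5: 18 × 0.75 = 13.5, taken as 13. Pooled placebo: 10 × 0.75 = 7.5, taken as 8. Intervals use the score method (Protocol 6.1.2). Reference rate: 30%-40%.

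**1. The plan's figure.** The score upper limit for 0/n is z²/(n + z²) with z² = 3.8415. For n = 4 it is 3.8415/7.8415 = 49.0%, which reproduces the protocol.

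**2. Against the reference rate.**

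| n with 0 responders | Upper limit |
|---|---|
| 4 | 49.0% |
| 5 (no missing data) | 43.4% |
| 6 | 39.0% |
| 9 | 29.9% |

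The limit first falls below 40% at n = 6 and below 30% at n = 9.

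**3. Chance of 0/4 with no loss.** (1 − p)⁴ is 0.7⁴ = 0.240 at 30% and 0.6⁴ = 0.130 at 40%.

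**4. Against the 20 mcg arm (4 vs 13).** Set the true Group 7 rate to 0%, so that the result is always 0/4. With 9/13 at 20 mcg, the two-sided Fisher p is C(8,4)/C(17,4) = 70/2380 = 0.029. With 8/13 it is (126 + 70)/2380 = 0.082. Power is therefore the probability of at least 9 responders of 13:

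| True 20 mcg rate | Fisher, standard | Fisher, doubled tail | Barnard |
|---|---|---|---|
| 30% | 0.4% | 0.1% | 1.8% |
| 40% | 3.2% | 0.8% | 9.8% |
| 60% | 35.3% | 16.9% | 57.4% |
| 75% | 79.4% | 58.4% | 92.0% |
| 94% | 99.9% | 99.4% | 100.0% |

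The doubled-tail test needs at least 10/13 and Barnard at least 8/13. The 20 mcg rate needed for 80% power is about 75%, 82% and 68% respectively.

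**5. Table 6-4.** All 9 × 14 outcomes of 8 vs 13 were enumerated. Entries are the Arm 2 rate (%) needed for 80%/90% power.

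| Arm 1 | Printed | Fisher, standard | Fisher, doubled tail | Arcsine, continuity-corrected |
|---|---|---|---|---|
| 0% | 64/73 | 54.0/59.9 | 61.3/67.0 | 63.5/73.0 |
| 10% | 79/87 | 73.6/80.5 | 76.4/83.6 | 78.7/86.7 |
| 20% | 89/95 | 83.4/89.6 | 87.1/92.4 | 88.5/94.9 |
| 30% | 96/– | 90.3/94.5 | 93.7/97.9 | 95.4/none |

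The arcsine power is Φ{2[asin√(p₂ − 1/(2n₂)) − asin√(p₁ + 1/(2n₁))] × √(n₁n₂/(n₁ + n₂)) − 1.96}. Taking the smallest whole percent that reaches the target, it reproduces every printed cell. It also explains the dash: at 30% vs 100% it gives 89.9%, just under 90%. At that point the enumerated power is 98.9% (standard) or 94.2% (doubled tail).

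**The case against.** **The comparator.** The sentence speaks of loss due to the lower dose, so the comparison is with infants at 20 mcg, and the 30%-40% adult range is introduced for the n = 13 power statement. The protocol hopes that infants respond better than adults. Primary endpoint 2 also includes gp120 binding, and Section 6.1.3 uses a high binding rate: "the (94%) response rate observed in the HVTN 088 vaccine recipients". Against 94%, 0/4 has probability 0.06⁴, about 0.00001, and the claim holds. This stands in part. The failure is conditional on the 20 mcg infant rate. But the sentence names neither a higher rate nor another endpoint, no infant lineage rate is given anywhere, and the 94% is not linked to Group 7.

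**The caveats.** The paragraph calls the arm unpowered and cursory, the protocol disclaims power across regimens, and the 49% limit is printed for all to see. This limits the harm. It does not repair a sentence that goes on to claim a specific capability.

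**Table 6-4.** The approximation is a recognised one and errs on the safe side, the gap to Fisher depends on the two-sided convention, and the analysis generally prefers Barnard's test. All true. The table still names a test whose enumeration gives other figures under either convention.

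**A stronger reading.** A reader might infer that the 82% and 77% infant rates in Section 6.1.3 are wrong too, because the same approximation reproduces them. The documents do not support that: 6.1.3 names no test for this binary comparison, so there is no stated method to contradict.

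**Conclusion.** The Group 7 claim does not hold at the only reference rate given for the response as defined. The interval after 0/4 runs to 49.0% and contains all of 30%-40%. The result would arise by chance 13%-24% of the time without loss, and even total loss would be detected against n = 13 with only 0.4%-3.2% standard Fisher power. This assumes that infants at 20 mcg respond near the adult lineage rate. At about 75% or more the claim becomes defensible, so it would be too strong to call it false for every endpoint. It is an overstated sentence about a descriptive arm and not a failed primary calculation, but it should be corrected.

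Table 6-4 is a secondary point. The printed rates exceed the enumerated ones by about 5 to 13 points (standard) or 2 to 6 (doubled tail), and the dash is wrong for the named test: 90% power is reached at about 94.5% or 97.9%. That the arcsine method was used is inferred from the match of all cells. A reader might infer that the vaccine-placebo comparison is in fact well powered. It is not: differences of 54 points or more are still needed, and both the low-power statement and the priority of the one-sample test stand.

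**What to change.** Reword the Group 7 sentence, for example: *n = 4 supports description only; 0 of 4 would exclude true response rates above 49% and would not by itself show a loss relative to a 30%-40% rate.* Alternatively, state the endpoint and the higher 20 mcg rate that the claim assumes.

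For Table 6-4, either name the approximation, or print enumerated Fisher figures with the two-sided convention stated. Under the standard convention, rounded up, these are 54/60, 74/81, 84/90 and 91/95, with 95 replacing the dash. The summary of about 70% would then become roughly 54-64 points at 80% power (54.0 − 0 to 73.6 − 10) and 60-71 points at 90% power (59.9 − 0 to 80.5 − 10).

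The cost is one sentence and either a method label or a few table figures. Section 6.1.3 needs no change on this account.

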This study will address this key question in infants and will be directly compared to similar data obtained in the adult participants in HVTN 115. Preliminary immunogenicity data collected after the third (of five total) immunizations with CH505TF in HVTN115 Part A (see schema Table 4-6) has been analyzed. Remarkably, a high percentage of CD4bs specific antibodies to the vaccine envelope were elicited, as detected by serum binding and B cell assays. Although there were no CD4bs or V2 glycan precursors detected by the specialized bnAb precursor neutralization assays, these data suggest that the right specificities were elicited early on and may be capable of further maturation. If, as hypothesized, the neonatal immune system is more permissive for the rapid development of bnAbs, it may be possible to elicit bnAbs in infants without sequential immunizations with lineage-directed immunogens.

Sequential immunization is a potential approach to achieve neutralization breadth

The Duke CHAVI-ID team described the co-evolution of HIV-1 and a CD4bs bnAb clonal lineage (CH103) in an African HIV-infected individual (CH505) (14). From this analysis, four evolutionarily related Envs were selected as vaccine immunogens (Figure 4-1). The safety and immunogenicity of this 4-valent sequential gp120 Env immunogen (EnvSeq-1), adjuvanted with GLA-SE, will be tested in a phase 1 adult trial (HVTN 115, Part B). Results from preclinical studies have provided support for sequential immunization strategies. Notably, CH505TF gp120 engaged a CD4bs bnAb germline B cell receptor on naïve B cells in CH103 bnAb knock-in mice (15). Moreover, sequential immunization of infant rhesus macaques with CH505 Env immunogens induced plasma neutralizing activity against their respective autologous viruses and recombinant memory B cell-derived monoclonal antibodies capable of neutralizing tier 2 HIV strains ([name] and [name] unpublished). As noted above, the critical question is how efficiently infant bnAb precursor B cells are expanded compared with adults. Overall, human and NHP data suggest that in infants, bnAb evolution may be achieved in a shorter time frame than in adults.

[figure not shown]

Figure 4-1 CH505 transmitted-founder (TF) and Env variants generated during viral evolution drove affinity maturation of CH103 bnAb lineage. Figure adapted from (14).

Development of broadly neutralizing antibodies in children

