4.4.3 Immunization number

Several interlinked considerations have informed the design of our study, utilizing five immunizations of CH505TF gp120 starting at birth, with the primary immunogenicity analysis at one year. These include: 1) to begin vaccination at birth to engage the unique qualities of the neonatal immune system, 2) the need to test for infant antibody responses at a timepoint where maternal antibodies have waned, and 3) to compare the infant immune response to the adult immune response in HVTN 115.

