4.5 Plans for future product development and testing

A goal of iterative human clinical trials to learn how to induce broadly neutralizing antibodies. This study will allow us to compare infant and adult immune responses to CH505TF gp120 and initiate the first steps in the CH103 bnAb lineage. Considerable data have been reported that bnAb precursors are rare and subdominant and, in some cases, are made so by tolerance controls of bnAb precursors in bone marrow (12, 50, 51). Thus, this trial represents the first in a potential series of iterative phase 1 clinical studies to begin learning how to induce bnAbs in infant vaccinees. Importantly, the match of the immunogens and adjuvants with Part A of the adult trial (HVTN 115) will address the question of whether infants respond differently than adults. Next steps following this trial will be informed by the results of the lineage based design strategy being tested in adults through HVTN 115 as well as several upcoming adult trials testing next generation immunogens which may stimulate bnAb lineages.

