The EnvSeq-1 immunogens consist of four gp120 proteins derived from CH505: CH505TF, CH505w53, CH505w78, and CH505w100. These proteins were administered to 3 groups of four rhesus macaques (NHP 79) with the GLA-SE adjuvant: 1) CH505TF Env gp120 alone; 2) the Envs given in a sequential regimen (CH505TF, CH505w53, CH505w78, and CH505w100); and 3) an additive-immunization regimen consisting of CH505TF gp120 in combination with the evolved Env variants (CH505TF, then CH505TF + CH505w53, then CH505TF + CH505w53 + CH505w78, then CH505TF + CH505w53 + CH505w78 + CH505w100). These Envs were research grade products made by transient transfection of 293 cells and have different glycosylation profiles than the CHO-produced CH505TF gp120s to be used in this clinical trial. This study demonstrates the proof of concept of using sequential Env variants in NHPs; the first step of this process using CH505TF is what will be tested in this clinical protocol. A follow on study employing the EnvSeq-1 immunogens administered in additive or sequential combinations may be a next step and will be informed by results from the HVTN 115 Part B trial which will test this approach in adults.

The CH505 gp120 Env derivatives (including CH505TF) were found to be immunogenic. An important readout in this study was the development of antibodies capable of binding a specific epitope on the CD4bs of the envelope protein. A defining feature of the CH103-like bnAbs is the capacity to bind wild type CH505 Env gp120 but not to CH505 Env with a deletion of isoleucine at aa position 371 (CH505 Env IΔ371 gp120). The data from the NHP 79 study suggest that the UCAs of bnAb lineages could be expanded by vaccination, but that they

did not evolve into bnAbs. In this study of 12 monkeys, 10/12 monkeys had differential binding antibodies isolated but overall the Env differential binding antibodies were subdominant and comprised only about 13% of the total activity of the antibody response, which is consistent with the low rate of bnAb development in HIV-infected adults (52) (Table 4-5).

Table 4-5 Frequency of antibodies isolated from CH505 envelope-vaccinated macaques. CH505 differential-binding antibodies (CH505 TF gp120+, CH505 TF gp120 Δ 371I+/- (greater than or equal to threefold vs. Wild Type)) were referred to as CH505 differentials. Adapted from Williams et al. (52).

		All antibody	lineages isola	ted		Unique clonal lineages				

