4.8 Clinical studies

4.8.1 Clinical studies of CH505TF gp120 with GLA-SE adjuvant in adults, HVTN 115

CH505TF gp120 is being evaluated in HVTN 115, the first clinical trial designed to use a B-cell lineage approach to elicit CD4bs bnAbs. In Part A, the dose ranging portion of HVTN 115, the CH505TF gp120 was administered at months 0, 2, 4, 8, and 12 at doses of 20, 100, and 400 mcg with 10 mcg of GLA-SE (Table 4-6).

Table 4-6 Schema for HVTN 115 Part A

Study group	N	Month 0 (Day 0)	Month 2 (Day 56)	Month 4 (Day 112)	Month 8 (Day 224)	Month 12 (Day 364)
1	12	20 mcg CH505TF	20 mcg CH505TF	20 mcg CH505TF	20 mcg CH505TF	20 mcg CH505TF
2	12	100 mcg CH505TF	100 mcg CH505TF	100 mcg CH505TF	100 mcg CH505TF	100 mcg CH505TF
3	12	400 mcg CH505TF	400 mcg CH505TF	400 mcg CH505TF	400 mcg CH505TF	400 mcg CH505TF
4	6	Placebo	placebo	placebo	Placebo	placebo
Total Part A	42 (36/6)					

Based on safety and immunogenicity data from Part A, HVTN 115 Part B will administer Env gp120 immunogens that induced a CD4bs bnAb clonal lineage in an HIV-infected individual in both sequential and additive strategies at a dose of 400mcg. The primary immune signal is differential binding antibodies between CH505TF Env gp120 (wild type) and CH505 Env I Δ 371 gp120 (mutant): a differential binding ratio of wild-type/mutant \geq 2.5 is characteristic of a CD4bs specificity.

HVTN 115 Part A reached full enrollment with 42 participants in May 2018. The last participant received their final vaccination on May 7, 2019. As of August 20, 2020, all scheduled study visits have been completed and the study remains blinded from a safety perspective. Most participants reported none or mild local signs and symptoms after vaccine administrations. There have been 2 cases of severe (grade 3) erythema/induration, which resolved within days. One of those participants experienced moderate injection site cellulitis, which resolved with oral antibiotics. Most participants reported none or mild systemic reactogenicity signs or symptoms after vaccinations. One case of severe (grade 3) pain at the injection site and two cases of severe (grade 3) headache were reported during the reactogenicity period. Beyond the reactogenicity period, there have been no severe adverse events related to study product.

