5.3 Exploratory objectives

Exploratory objective 1:

To compare antibody and B cell responses generated in infants in response to CH505TF gp120 adjuvanted with GLA-SE with adults vaccinated with the same immunogen and same adjuvant on the same schedule (HVTN 115)

Exploratory objective 2:

To characterize B cell lineages and evaluate the amount of B-cell receptor somatic hypermutation

Exploratory objective 3:

To evaluate effects of maternal antibody in cord blood, serum/plasma, and breast milk on the humoral response of infants

Exploratory objective 4:

To evaluate additional vaccine-induced antibody effector functions such as Antibody-dependent neutrophil phagocytosis (ADNP) and/or Antibody dependent complement deposition (ADCD)

Exploratory objective 5:

To measure the kinetics and maturation of the polyclonal antibody response with biophysical measurements (eg, BioLayer Interferometry, Surface Plasmon Resonance)

Exploratory objective 6:

Evaluation of breast milk and fecal microbiome at birth and over time to explore the effect of the microbiome on the development of the immune system and on vaccine immunogenicity

Exploratory objective 7:

To use systems biology approaches (eg, high resolution flow cytometry. transcriptomics, proteomics, metabolomics and/or plasma cytokine/chemokine assessment) to determine whether the pre- and/or postvaccination systemic immune milieu is associated with vaccine immunogenicity.

Exploratory objective 8:

To further evaluate immunogenicity, additional assays may be performed based on the HVTN Lab Assay Algorithm

Exploratory objective 9:

To conduct analyses related to furthering the understanding of HIV, immunology, vaccines, and clinical trial conduct

6 Statistical considerations

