To address Exploratory Objective 1 (comparison to adults), the analysis will descriptively summarize binding response positivity call rates, and test superiority of the frequency of differential memory B cell binding (to wild type vs mutant I Δ 371 CH505) and of the magnitude and breadth of the IgG binding Ab response to a panel of gp120 proteins using a two-sided Wilcoxon rank sum test with 5% type-I error rate per comparison. This exploratory objective involves a comparison across populations (infants versus adults, in different demographic settings). Since this factor is necessarily non-randomizable, these comparisons are of the "observational" category, in the sense that they do not share the statistical benefits of the randomized controlled clinical trial design. Specifically, while the "study" factor differentiates adults from infants, these cohorts differ in many other respects. Therefore, the interpretation of any differences observed will require more careful consideration of the potential confounding effects of measured and unmeasured differences across the populations besides the age of the vaccine recipient.

Immunogenicity in the HVTN 115 Part B vaccine recipients (n = 20 per group, n = 60 total), pooled with the corresponding dose group from Part A (n = 12) will be compared to immunogenicity in the HVTN 135 vaccine recipients. After an expected 15% of immunogenicity data missingness in HVTN 115 at the immunogenicity timepoint post 5th vaccination (at one year), sample sizes for comparisons across these study populations will be approximately n = 13 infants vs n = 27 (one HVTN 115 Part B arm, and one HVTN 115 Part A arm) or n = 61 (all 3 Part B vaccine arms, and 1 Part A arm). Comparisons are well-powered under this scenario for both binary responses and for comparisons of continuous responses (eg measuring antibody binding magnitudes). If the true response rate in adults is 30%, there is 80% power to detect a difference vs infant response rates if the true rate in infants is 82% or greater when comparing to n = 27 adults, and there is 80% power to detect a difference vs n = 61 adults when the true rate in infants exceeds 77%.

For continuous endpoints, there is 80% power to detect a difference across adult vs infant groups of 1.16 standard deviations (SDs) when considering n = 27 adults, and 1.04 SDs when considering n = 61 adults. As a point of reference,

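### The n = 61 adult set for the infant–adult comparison puts sequential and additive Env arms into a same-immunogen contrast, so it mixes age with vaccine regimen

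*Protocol*

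**What the plan says.** Protocol 5.3, repeated in SAP 3.3, sets Exploratory Objective 1 as a comparison with "adults vaccinated with the same immunogen and same adjuvant on the same schedule (HVTN 115". Protocol 4.5 relies on "the match of the immunogens and adjuvants with Part A of the adult trial (HVTN 115" to answer whether infants respond differently from adults. Protocol 4.4.3 lists among its design considerations "to compare the infant immune response to the adult immune response in HVTN 115".

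Protocol 6.1.3 defines the adult side. Part B recipients (20 per group, 60 in total), "pooled with the corresponding dose group from Part A (n = 12) will be compared to immunogenicity in the HVTN 135 vaccine recipients". After 15% missing data this gives two alternatives: 27 adults (one Part B arm plus one Part A arm) or "n = 61 (all 3 Part B vaccine arms, and 1 Part A arm".

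Part B is described elsewhere as a different vaccine strategy. Protocol 4.1 says the four-valent EnvSeq-1 product, "adjuvanted with GLA-SE, will be tested in a phase 1 adult trial (HVTN 115, Part B". Protocol 4.8.1 says Part B gives its Env immunogens "in both sequential and additive strategies at a dose of 400mcg". Protocol 4.7.2 says a follow-on study of EnvSeq-1 "administered in additive or sequential combinations may be a next step and will be informed by results from the HVTN 115 Part B trial". No section lists the three Part B arms.

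SAP 9.5 mentions the infant–adult comparison but names no adult arms, and its outputs contain no adult contrast. The objectives listed in SAP 9.3 for BAMA do not include Exploratory Objective 1.

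**The concern.** A comparison meant to isolate age should hold the immunogen fixed. The n = 61 set does not. Most of its adults come from Part B, and the Part B strategies named in the protocol add or substitute other Env proteins. If infants and adults differ in that contrast, or fail to differ, the result could reflect age, Env regimen or both.

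Protocol 6.1.3 does warn about confounding, but its warning concerns differences between the populations, which cannot be randomised away. Regimen is another matter, because the analyst chooses which adult arms to include. The comparison with adults is also part of the trial's stated rationale (Protocol 4.4.3 and 4.4.4).

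**Working it through.** **Inputs.** Part B: 3 arms × 20; one Part A group: 12; missing data 15% in adults (Protocol 6.1.3). Part A: three groups of 12 at 20, 100 and 400 mcg, with 10 mcg GLA-SE (4.8.1). Infants: Groups 3+5, 20 mcg with 5 mcg GLA-SE, 18 × 0.75 = 13.5, printed as 13 (6.1.2, 8.1). Test: two-sided 5% Wilcoxon; 6% zero values; adult response rate 30% (6.1.3).

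**1. The plan's sample sizes reproduce.** (20 + 12) × 0.85 = 27.2 and (60 + 12) × 0.85 = 61.2.

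**2. Share of adults on another regimen.** Using both strategies needs at least one sequential and one additive arm.
- n = 61, two arms differ: 40/72 = 56%; all three differ: 60/72 = 83%.
- n = 27: 0% if the chosen Part B arm is CH505TF-only, otherwise 20/32 = 63%.

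**3. Which Part A group.** 6.1.3 calls for the group whose dose corresponds to Part B, and 4.8.1 puts Part B at 400 mcg. That points to the 400 mcg group, against 20 mcg in infant Groups 3+5. The 20 mcg Part A arm, the only one matched on protein dose, would be left out.

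**4. What a CH505TF-only set would cost.** Binary endpoint: two-sided Fisher test, full enumeration, 13 infants, adults at 30%. Continuous endpoint: simulated Wilcoxon, non-zero values normal with mean 4.05 and SD 0.38/1.04 = 0.365, 6% zeros, shift applied to non-zero values. Detectable at 80% power:

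| Adult set | Adults | Infant rate | Shift (SD) |
|---|---|---|---|
| Part A, 20 mcg only | 12 × 0.85 = 10.2, taken as 10 | 87.0% | 1.57 |
| One Part B + one Part A arm | 27 | 76.4% | 1.19 |
| All Part A vaccinees | 36 × 0.85 = 30.6, taken as 31 | 76.4% | 1.17 |
| All Part A + one Part B arm | 56 × 0.85 = 47.6, taken as 47 | 74.9% | 1.10 |
| Three Part B + one Part A arm | 61 | 73.5% | 1.07 |

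The protocol prints 1.16 SD (27 adults) and 1.04 SD (61). A check at those values gave about 79% and 78% power, so they reproduce closely. Read as differences in overall means (× 0.94), the simulated shifts are roughly 1.12 and 1.0, so the two readings bracket the printed values. The printed binary rates, 82% and 77%, are conservative: Fisher power there is about 90% and 87%. Nothing here rests on them.

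**5. Illustration only.** The documents give no human regimen effect, so one is assumed. If infants truly equal CH505TF-only adults, the nominal 5% Wilcoxon test against 61 adults rejects as follows (40 × 0.85 = 34 or 60 × 0.85 = 51 adults shifted):

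| Assumed regimen effect | 34 of 61 shifted | 51 of 61 shifted |
|---|---|---|
| 0 | 5% | 5% |
| 0.2 SD | 6% | 7% |
| 0.5 SD | 11% | 20% |
| 1.0 SD | 28% | 61% |

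For a true infant advantage of 1.07 SD, power falls from 80% to 72%–69% (0.2 SD) or 56%–43% (0.5 SD) if the other regimens respond higher. If they respond lower by 0.5 SD, it rises spuriously to 92%–95%.

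The same test can be applied to pooling all Part A doses, where 24/36 = 67% received 100 or 400 mcg. Shifting 21 of 31 adults gives rejection of about 12% at 0.5 SD and 34%–35% at 1.0 SD.

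**The case against.** Several counter-arguments have weight.

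- **6.1.3 is a sizing section with two alternatives.** It does not make n = 61 the main contrast, and it already labels the comparison observational. This stands, and it limits the consequence. It does not remove the conflict, because regimen is not among the differences it warns about and no other section chooses between the two sets.
- **The Part B design is not shown.** The 56% is an inference from two named strategies, not a count of listed arms. Table 4-8 (March 2018) lists 116 GLA-SE recipients in HVTN 115. Less the 36 Part A vaccinees, that leaves 80, against 60 in 6.1.3, so the Part B structure is uncertain here. This stands as a reason to confirm the arms.
- **The regimen effect may be small.** In the macaque study (Table 4-5), differential-binding antibodies were 13/106 (12%) for CH505TF alone, 6/62 (10%) sequential and 17/110 (15%) additive. With four animals per group this settles nothing, but it is a fair reason not to lean on the larger assumed effects.
- **A Part A pool is itself mixed.** Step 5 shows that equal assumed dose effects would distort it about as much as the lower bound for n = 61. Protocol 4.8.1 reports no statistically significant dose differences, but with 12 per group that does not show equality, and 6.1.2 cites response rates of 30%–40% varying by dose. This stands and shapes the fix.
- **The SAP's silence is not particular to this objective.** Other exploratory objectives also lack dedicated outputs, and SAP 9.5 frames the comparison as responses to CH505TF gp120. Both points are fair; the adult arms still need naming somewhere.

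**Conclusion.** The conflict holds for the n = 61 set: it pools all three Part B arms into a same-immunogen contrast, so at least 56% of its adults, by inference, and up to 83%, were not on CH505TF alone. For n = 27 the finding is one of ambiguity: the Part B arm is unidentified (0% or 63% on another regimen), and the Part A group, by inference 400 mcg, differs in protein dose from the infants.

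A reader might infer more than the documents support:
- *That both adult sets are confounded by regimen.* A CH505TF-only Part B arm joined to the 400 mcg Part A group would be homogeneous in regimen and protein dose.
- *That the Part A dose group is an open choice.* It is not named, but 6.1.3 read with 4.8.1 points to 400 mcg.
- *That false-positive rates of 11%–61% are to be expected.* They follow only from assumed regimen effects of 0.5 to 1.0 SD; at 0.2 SD the rate is 6%–7%.
- *That the trial's main conclusions are at risk.* The objective is exploratory and non-randomised, and no primary or secondary endpoint is touched.

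**What to change.** In Protocol 6.1.3 and the SAP:

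1. Name the arms on both sides. Infants: Groups 3+5 (about 13). Adults in the same-immunogen contrast: only arms that received CH505TF gp120 alone, meaning Part A, plus a Part B arm only if it is confirmed CH505TF-only.
2. Report sequential and additive Part B arms separately, labelled as a different regimen.
3. Show the Part A results by protein dose, with the 20 mcg arm (about 10 adults) as the dose-matched contrast.
4. State the remaining protein-dose differences and the GLA-SE difference (10 mcg in Part A adults, 5 mcg in Groups 3+5) as limitations.
5. Restate the detectable differences for the set chosen and name the test behind each. For 27 to 31 adults these are about 76% against 30% (Fisher) and 1.17–1.19 SD (Wilcoxon, 6% zeros).
6. Add the contrast to the SAP outputs, or cite the plan that will hold it.

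This changes wording only; Protocol 4.8.1 reports Part A visits complete by August 2020. The price is the n = 61 scenario: the detectable difference rises from about 1.07 to 1.17–1.19 SD and the detectable infant rate from 73.5% to 76.4%. A confirmed CH505TF-only Part B arm added to all Part A vaccinees (about 47 adults) recovers part of this: 74.9% and 1.10 SD. The 20 mcg arm alone is weak (87% or about 1.57 SD) and should be read descriptively.
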